7.3.3.2 Covariates for myotoxicity

The presence of the following variables will be assessed at the index date:

- Obesity (in year prior to index date)
- Hypothyroidism (in year prior to index date)
- Hypovitaminosis D (in year prior to index date)
- Chronic renal insufficiency (any time prior to index date)
- Infections (in 90 days prior to index date)
- Liver impairment (in year prior to index date)
- Alcohol abuse (in year prior to index date)
- Surgery (in 90 days prior to index date)
- Metabolic disorders (any time prior to index date)

Codes, drugs and algorithms to identify these covariates will be developed and described in the SAP.

7.3.3.3 Covariates for hepatotoxicity

- Drugs causing acute or cholestatic hepatotoxicity (within 90 days before index date): e.g. isoniazid, pyrazinamide, rifampicin, ibuprofen, nimesulide, cotrimoxazole, phenytoin, dapsone, chlorpromazine, amoxicillin-clavulanic acid, flucloxacillin, carbamazepine, phenytoin, fluoroquinolones, acetaminophen [paracetamol]) ([Devarbhavi and Andrade 2014](#))
- Alcohol abuse (in year prior to index date)
- HIV infection (in year prior to index date)

Codes, drugs and algorithms to identify these covariates will be developed and described in the SAP.

7.3.3.4 Covariates for acute pancreatitis

- Gallbladder disease (gallstones) (in year prior to index date)
- Alcohol abuse (in year prior to index date)
- Hypercalcemia (in year prior to index date)
- Hypertriglyceridemia (in year prior to index date)
- Trauma (90 days prior to index date)
- Endoscopic retrograde cholangiopancreatography (ERCP) (90 days prior to index date)

- Cholecystectomy (90 days prior to index date)
- Drugs associated with acute pancreatitis including ACEIs (90 days prior to index date) (Jones et al 2015)

Codes, drugs and algorithms to identify these covariates will be developed and described in the SAP.

7.4 Data sources

This study will be conducted by using five European databases that comprise routine health care data. This will provide a reflection of real-world circumstances and prescribing behaviors. The databases have been selected based on their geographic location, the availability of population-based data on drugs, plus their recognized reputation in the area of drug utilization and safety research. Multiple countries are included in order to provide international data and to guarantee sufficient exposure to LCZ696.

The data for this study will be retrieved from The Clinical Practice Research Datalink (CPRD) from the UK and will be used through a Novartis license, the Sistema d'Informació per al Desenvolupament de la Investigació en Atenció Primària' (SIDIAP) from Spain provided by IDIAP Jordi Gol, the Health Search CSD Longitudinal Patient Database (HSD) from Italy provided by Società Italiana di Medicina Generale, the PHARMO Database Network (PHARMO) from the Netherlands provided by the PHARMO Institute for Drug Outcomes Research, and the Aarhus University Prescription Database from Denmark provided by Aarhus University.

All analyses will be performed in collaboration between [REDACTED], the scientific lead, and [REDACTED], the coordinating centre for the study according to contractual agreements.

Table 7-5 provides an overview of database characteristics including the available data. These databases have a mean follow-up ranging from 2.5 to 11 years. The databases are representative of the country-specific populations in terms of age and gender. The databases that will be used are primary care databases (except for the Aarhus database from Denmark and PHARMO from the Netherlands) and available data are complete as they come from the general practitioners' [GPs] electronic primary care records. The primary care databases represent 3-20% of the country specific total population. The total number of persons in the source population encompassing all five databases will be around 16 million in 2016.

Table 7-5 Overview of databases to be used for the study

Characteristic	Database				
	PHARMO	CPRD	Aarhus	HSD	SIDIAP
Country	Netherlands	United Kingdom	Denmark	Italy	Spain
Type of database	EMR	EMR	ADM	EMR	EMR
Number of patients, millions	1.2*	5.7 (approx. 55% linked to HES data)	1.8	1.5	5.1 (1.7 linked to hospital data)
Date in	Yes	Yes	Yes	Yes	Yes

Characteristic	PHARMO	CPRD	Database		
			Aarhus	HSD	SIDIAP
Date out	Yes	Yes	Yes	Yes	Yes
Date of death	Yes	Yes	Yes	Yes	Yes
Cause of death	No	Yes	Yes	No	No
Updates	Annual (October)	Monthly (2-times a year for HES)	Yearly (April)	2-times a year: (30/06 and 31/12)	Yearly (April/May)
Prescriptions					
Outpatient Rx	Yes	Yes (specialist incomplete)	Yes	Yes (specialist incomplete)	Yes (specialist incomplete)
Coding of drugs	ATC	BNF/Multilex code	ATC	ATC	ATC
Dosing regimen	Yes	Yes	No	Yes (incomplete)	Yes
Outcomes					
Hospitalizations	Yes	Yes	Yes	Yes	Yes (for 1.7 mio linked patients)
Outpatient diagnoses	Yes	Yes	Yes	Yes	Yes
Coding of disease	ICPC, ICD-10	READ (ICD-10 for HES data)	ICD-10	ICD-9 CM	ICD-10 (ICD-9 for hospital data)
Laboratory data	Yes	Yes	yes	Yes	Yes

ADM = Administrative; ATC = Anatomical Therapeutic Chemical; BNF = British National Formulary; CPRD = Clinical Practice Research Datalink; EMR = Electronic Medical Records; HES = Hospital Episode Statistics; HSD = Health Search CSD Longitudinal Patient Database; ICD= International Classification of Disease, ICPC = International Classification of Primary Care; Rx = prescription; SIDIAP = Sistema d'Informació per al Desenvolupament de la Investigació en Atenció Primària
* GP and out-patient pharmacy data

All of the databases comply with EU guidelines on the use of medical data for medical research and have been validated for pharmacoepidemiological research ([Ehrenstein et al 2010](#), [van Herk-Sukel et al 2010](#), [Cazzola et al 2011](#), [Garcia-Gil et al 2011](#), [Herrett et al 2010](#), [Jick et al 2003](#)).

More details on the individual databases are provided in the following sections.

7.4.1 Clinical Practice Research Database (CPRD) – UK

The CPRD; from the UK collates the computerized medical records of general practitioners (GPs) in the UK who act as the gatekeepers of healthcare and maintain patients' life-long electronic health records. As such they are responsible for primary healthcare and specialist referrals, and they also store information stemming from specialist referrals, and hospitalizations. The data recorded in the CPRD include demographic information, prescription details, clinical events, preventive care, specialist referrals, hospital admissions, and major outcomes, including death. The majority of the data are coded in READ Codes

(Booth 1994); however, additional text data is also available, which can improve the sensitivity and specificity of data. Validation of data with original records (specialist letters) is also available.

Importantly, CPRD operates a careful and continual quality control procedure that ensures that only practices that are “up-to-standard” (UPS) are included in the research dataset. The dataset is generalizable to the UK population based upon age, sex, socioeconomic class and national geographic coverage.

There are currently approximately 13.2 million patients (acceptable for research purposes) – of which 5.7 million are active (still alive and registered with the GP practice) – in approximately 680 practices. Data include demographics, all GP/healthcare professional consultations (phone, letter, email, in surgery, at home), diagnoses and symptoms, laboratory test results, treatments, including all prescriptions, all data referrals to other care, hospital discharge summary (date and ICD code), hospital clinic summary, preventive treatment and immunizations, death (date and cause). For a proportion of the CPRD panel practices (~55%), the GPs have agreed to permit CPRD to link at patient level to the Hospital Episode Statistics (HES) data.

The HES is a data warehouse containing details of all admissions to National Health Service (NHS) hospitals in England (~168 acute NHS Trusts) collected by the Health & Social Care Information Centre. HES is the data source for a wide range of healthcare analysis for the NHS, government and many other organizations and individuals. The HES database contains dates of hospital admissions, primary and secondary diagnoses (coded using the ICD-10 classification), and related procedures (coded using the ICD-10 classification and Office of Population Censuses and Surveys Classification of Interventions and Procedures, Fourth Version). Linked data can be analyzed over a period from January 1997 up to the most recent available HES year (1-2 years delay).

CPRD is listed under the ENCePP resources database (www.encepp.eu/encepp/resourcesDatabase.jsp).

7.4.2 Sistema d'Informació per al Desenvolupament de la Investigació en Atenció Primària' (SIDIAP) – Spain

GPs play an essential role in the public health care system of Spain, as they are responsible for primary health care, long-term prescriptions and specialist and hospital referrals. The Spanish public health care system covers more than 98% of the population. The SIDIAP database comprises of electronic medical records of a representative sample of patients attended by GPs in Catalonia (North-East Spain), covering a population of more than 5.1 million patients (about 80% of the total of 7.5 million population of Catalonia) from 274 primary care practices with 3,414 participating GPs. The SIDIAP data comprises the clinical and referral events registered by primary care health professionals (GPs and nurses) and administrative staff in electronic medical records, comprehensive demographic information, prescription and corresponding pharmacy invoicing data, specialist referrals, and primary care laboratory test results. Hospital admissions and their major outcomes can be identified for a number of practices, covering a total 1.7 million active patients. Health professionals gather this information using ICD-10 codes (primary care records) and ICD-9 (hospital admissions), and

structured forms designed for the collection of variables relevant for primary care clinical management, such as country of origin, sex, age, height, weight, body mass index, tobacco and alcohol use, blood pressure measurements, blood and urine test results. Only GPs who meet quality control standards can participate in the SIDIAP database. Encoding personal and clinic identifiers ensures the confidentiality of the information in the SIDIAP database. Recent reports have shown the SIDIAP data to be useful for epidemiological research ([Garcia-Gil et al 2011](#)).

As this is a primary care database, information on specialist prescribing, drug dispensing and actual drug intake is missing.

SIDIAP is listed under the ENCePP resources database (www.encepp.eu/encepp/resourcesDatabase.jsp).

7.4.3 Health Search CSD Longitudinal Patient Database (HSD) – Italy

The Italian arm of the study will use the Health Search CSD Longitudinal Patient Database (HSD), a longitudinal observational database that is representative of the Italian general population. It was established in 1998 by the Italian College of General Practitioners ([Filippi et al 2005](#)). The HSD contains data from computer-based patient records from a selected group of GPs (covering a total of 1.5 million patients) located throughout Italy. These GPs voluntarily agreed to collect data for the database and attend specified training courses. The database includes information on the age, gender, and identification of the patient, and GP registration information, which is linked to prescription information, clinical events and diagnoses, hospital admission, and causes of death. Laboratory values are available. All diagnoses are coded according to the International Classification of Diseases, 9th Revision, Clinical Modification (ICD-9-CM). Drug names are coded according to the ATC classification system. To be included in the study, GPs must have provided data for at least 1 year and meet standard quality criteria pertaining to: levels of coding, prevalence of well-known diseases, and mortality rates ([Cricelli et al 2003](#)). The HSD complies with EU guidelines on the use of medical data for research. The HSD has been used as data source for a number of peer reviewed publications on the prevalence of disease conditions, drug safety and prescription patterns in Italian primary care ([Cazzola et al 2011](#)). Approval for use of data is obtained from the Italian College of General Practitioners.

Dose must be inferred from the strength and according to the dosing regimens of the respective Summary of Product Characteristics (SmPC) for the other drugs. Around 50% of prescription dosage is also imputed by GPs.

As this is a primary care database, information on specialist prescribing, drug dispensing and actual drug intake is missing.

HSD is listed under the ENCePP resources database (www.encepp.eu/encepp/resourcesDatabase.jsp).

7.4.4 PHARMO Database Network (PHARMO) – the Netherlands

The PHARMO Database Network is a population-based network of electronic healthcare databases and combines data from different primary and secondary healthcare settings in the Netherlands. These different data sources, including data from general practices, in- and out-

patient pharmacies, clinical laboratories, hospitals, the cancer registry, pathology registry and perinatal registry, are linked on a patient level through validated algorithms. Detailed information on the methodology and the validation of the used record linkage method can be found elsewhere ([van Herk-Sukel et al 2010](#)).

The longitudinal nature of the PHARMO Database Network system enables to follow-up more than 4 million (25%) residents of a well-defined population in the Netherlands for an average of ten years. Data collection period, catchment area and overlap between data sources differ. Therefore, the final cohort size for any study will depend on the data sources included. As data sources are linked on an annual basis, the average lag time of the data is one year. All electronic patient records in the PHARMO Database Network include information on age, sex, socioeconomic status and mortality. Other available information depends on the data source. To address the objectives of the present study the following PHARMO databases will be used: General Practitioner Database, Out-patient Pharmacy Database and Hospitalisation Database.

The General Practitioner (GP) Database comprises data from electronic patient records registered by GPs. The records include information on diagnoses and symptoms, laboratory test results, referrals to specialists and healthcare product/drug prescriptions. The prescription records include information on type of product, prescription date, strength, dosage regimen, quantity and route of administration. Drug prescriptions are coded according to the WHO Anatomical Therapeutic Chemical (ATC) Classification System. Diagnoses and symptoms are coded according to the International Classification of Primary Care (ICPC), which can be mapped to ICD codes, but can also be entered as free text.

The Out-patient Pharmacy Database comprises GP or specialist prescribed healthcare products dispensed by the out-patient pharmacy. The dispensing records include information on type of product, date, strength, dosage regimen, quantity, route of administration, prescriber specialty and costs. Drug dispensings are coded according to the WHO Anatomical Therapeutic Chemical (ATC) Classification System.

The Hospitalisation Database comprises hospital admissions for more than 24 hours and admissions for less than 24 hours for which a bed is required from the national Dutch Hospital Data Foundation. The records include information on hospital admission and discharge dates, discharge diagnoses and procedures. Diagnoses are coded according to the WHO International Classification of Diseases (ICD) and procedures are coded according to the Dutch Hospital Data Foundation registration system for procedures which links to the Dutch Healthcare Authority (NZa) declaration codes and the Dutch Classification of Procedures.

Combined GP, Out-patient Pharmacy and Hospitalisation data currently cover a catchment area representing 1.2 million residents.

PHARMO is listed under the ENCePP resources database (www.encepp.eu/encepp/resourcesDatabase.jsp).

7.4.5 Aarhus University Prescription Database – Denmark

The Aarhus University Prescription Database comprises clinical and prescription data on the population of former North-Jutland, Aarhus, Rinkjebing and Viborg counties, which since 2007 are called the Central Denmark Region and the North Denmark Region. This population covers a total of 1.8 million inhabitants and is representative of the population of Denmark

(Ehrenstein et al 2010). Data available on these subjects comprise their eligibility, dispensing data, hospitalizations and procedures and the population can also be linked to other National Danish registries. Dispensing data comprise the filled prescriptions for all ambulatory patients and contains information on name of the drug, ATC code, package identifier (strength and route of administration), and the date of refill. These data can be linked to the national registry of patients that comprises information on admissions to Danish somatic hospitals, emergency rooms and outpatient clinics, diagnosis codes and procedures are registered. These databases have been used in numerous studies and are proven valid for pharmacoepidemiological research (Sørensen and Larsen 1994).

Dose must be inferred from the strength, and according the dosing regimens of the respective SmPC of the other drugs. The main drawbacks of the Aarhus University Prescription Database are a lack of nationwide coverage and the absence of data of certain medication types (non-reimbursed drugs, OTC drugs or drugs dispensed directly to hospital patients or outpatient clinics).

Aarhus is listed under the ENCePP resources database (www.encepp.eu/encepp/resourcesDatabase.jsp).

7.5 Study size/power calculation

The sample size is calculated following a non-inferiority approach (Wang and Chow 2007), with the intent to demonstrate that the increased risk due to LCZ696 exposure is less than 3-fold for hepatotoxicity and less than 5-fold for myotoxicity or acute pancreatitis.

Forty cases with hepatotoxicity will allow ruling out a 3-fold increased risk with a one-sided test (80% power, 5% type I error), assuming a conservative case:control ratio of 1:4 and conservatively, that 20% of the statin-exposed HF patients concomitantly use LCZ696 in the control group (Table 7-6).

Assuming an incidence rate of acute hepatic events in statin-treated HF patients of 6.1 and 12.9/10,000 PYs (Cziraky et al 2006), the underlying study base is expected to be comprised of at least about 66,000 and 31,000 patient-years (PYs), respectively.

A total of 19 cases with a myotoxic event will allow ruling out a 5-fold increased risk (Table 7-6). Assuming IR of myopathy in statin-treated HF patients between 2.3 and 9/10,000 PYs (Macedo et al 2014), the underlying study base should comprise of at least about 83,000 and 21,000 PYs, respectively.

The underlying study base should comprise of at least about 38,000 PYs in order to observe 19 cases of acute pancreatitis assuming an IR of statin-associated acute pancreatitis of 5/10,000 PYs (Kuoppala et al 2015).

Table 7-6 Sample size scenarios for a one-sided non-inferiority test (80% power, 5% type 1 error)

[figure not shown]
Risk to be ruled out	No of cases needed	
	with 10% LCZ696 use	with 20% LCZ696 use
5	33	19
3	71	40

Risk to be ruled out	No of cases needed	
	with 10% LCZ696 use	with 20% LCZ696 use
2	179	100

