7.2.2.3 Start and end of follow-up

Follow-up for each subject in the study base will start at the latest of the following points in time:

- Start date of LCZ696 launch
- Reaching age 18 years
- Having at least one year of valid data in the database (to allow for assessment of co-morbidities)

Follow-up ends at the earliest of the following dates:

- Last data download in practice
- Date that the patient transfers out of the database
- Date of death

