7.7.2 Final analysis

The final analysis based on validated cases will be conducted at the end of the study (after reaching the necessary number of cases) and is expected to be submitted in Q2 2020.

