7.7.2.3 Primary and secondary analyses

Conditional logistic regression analyses will be used to estimate crude and adjusted relative risks (expressed as odds ratios [ORs]) of each specific outcome with corresponding 95% confidence intervals (CIs).

The primary analysis is current LCZ696 and statin versus current use of statin (any dose) without current use of LCZ696.

Secondary analyses comprise investigation of dose of statin and duration of LJC696, recent use of LJC696 or statins, and individual statins. In the dose specific analysis for statins the reference category will be current low dose of statins and non-use of LJC696.

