For all databases, apart from Aarhus University Prescription Database, it should be noted that the primary aim of data collection is patient management and not medical research. This implies that only events are collected which are deemed to be relevant to the patient's care. In addition, specialist information is incomplete in the majority of the databases. Aarhus and PHARMO contain all reimbursed prescriptions from GPs and specialists. The other databases are primary care databases, so they may not capture all prescriptions of specialists. However, in all of these countries (UK, Italy, and Spain), the GP is the gatekeeper of care and prescriptions initiated by the specialist are continued by the GP. Missing information on LCZ696 exposure may lead to some misclassification of duration in the secondary analyses.

None of the databases will be able to capture over-the-counter (OTC) drug use. This may be relevant for instant with respect to use of acetaminophen in the context of hepatotoxicity, as most acetaminophen use will be OTC and prescription use will be limited.

Finally, there are differences in timing of data updates in the various databases (medical records are continuously updated, administrative databases are updated only once per year in most instances). However, as data-extraction will be repeated during the course of the study, this should allow for “up-to-date data” at study end.

The most important uncertainty is about the uptake of LCZ696, which may limit the power of the study.

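### The 20% LCZ696 use behind the 40- and 19-case targets is called conservative, but it is the more favourable tabulated scenario and has no uptake data behind it; the targets should be conditional on observed exposure

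*Protocol*

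**What the plan says.** Section 7.5 sets the purpose of the calculation: "The sample size is calculated following a non-inferiority approach", to show that the increase in risk is "less than 3-fold for hepatotoxicity and less than 5-fold for myotoxicity or acute pancreatitis". The test is one-sided at 5% with 80% power and four controls per case. The exposure input is "conservatively, that 20% of the statin-exposed HF patients concomitantly use LCZ696 in the control group". The resulting targets are 40 cases for hepatotoxicity and 19 each for myotoxicity and acute pancreatitis. Table 7-6 also has a 10% column, which needs 71 and 33 cases. The abstract repeats 40 and 19 and the conservative label, without the 10% alternative.

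Four other places bear on the exposure input:

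- Section 7.2.2.3 lists "Start date of LCZ696 launch" among the dates that can open follow-up. Table 7-1 puts launch between December 2015 and October 2016.
- Section 7.2.2.4.1 gives each control the calendar date of its case and matches all available controls.
- Section 7.7.2 places the final analysis "after reaching the necessary number of cases".
- Section 7.9 says: "The most important uncertainty is about the uptake of LCZ696, which may limit the power of the study".

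Section 7.7.2.3 reports odds ratios with 95% confidence intervals. It does not say which limit decides whether a risk is ruled out.

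**The concern.** In a matched case-control study, information about the exposure odds ratio depends on how many sets contain both exposed and unexposed members. A case indexed soon after launch sits in a set with almost no LCZ696 user. It adds almost nothing to the estimate, yet it counts as one full case towards the target.

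Other statements in the protocol also give reason to expect low recorded use. The product is indicated for reduced ejection fraction (section 5), whereas cases and controls need only a heart failure diagnosis (section 7.2.2.4.1). Specialist prescriptions are incompletely captured in CPRD, HSD and SIDIAP (Table 7-5), and section 7.9 notes that specialists may start the drug.

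At stake is a safety conclusion. The study could report that its size requirement was met while holding little more than half the planned information. Failure to exclude a 3-fold or 5-fold risk would then reflect a shortage of exposed patients and not a signal.

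**Working it through.** **Inputs from section 7.5.** Margin M = 3 or 5; one-sided α = 0.05 (z = 1.645); power 0.80 (z = 0.842); k = 4 controls per case; exposure among controls p = 0.20 or 0.10. The true odds ratio is not stated. It is taken as 1, which reproduces the table.

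**Step 1: reproduce Table 7-6.** Cases = (z₁₋α + z_power)² × (1 + 1/k) / [ln(M)² × p(1−p)]. With unrounded quantiles the numerator is 6.183 × 1.25 = 7.728.

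- p = 0.20, M = 3: 7.728 / (1.207 × 0.16) = 40.02 (printed 40)
- p = 0.20, M = 5: 7.728 / (2.590 × 0.16) = 18.65 (printed 19)
- p = 0.10, M = 3: 71.15 (printed 71)
- p = 0.10, M = 5: 33.15 (printed 33)
- M = 2: 100.53 at 20% (printed 100) and 178.72 at 10% (printed 179)

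All six entries reproduce to within one case.

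**Step 2: power at the targets on the stated inputs.** Power = Φ(ln(M) × √[cases × v/(1 + 1/k)] − z₁₋α), with v = p(1−p).

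- 40 cases, M = 3: Φ(1.0986 × √5.12 − 1.645) = 80.0%
- 19 cases, M = 5: Φ(1.6094 × √2.432 − 1.645) = 80.6%

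**Step 3: vary exposure.** The protocol gives no uptake figure, so the rows below are assumptions that show a range. For linear uptake from 0 to b over index dates, v becomes the mean of p(1−p), which is b/2 − b²/3. For b = 0.20, v = 0.1 − 0.0133 = 0.0867, or 54% of the planned 0.16. Each pair is 40 cases/3-fold, then 19 cases/5-fold, at one-sided 5%.

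| LCZ696 use over index dates | v | Power at 1:4 | Upper bound, very many controls | Cases for 80% at 1:4 |
|---|---|---|---|---|
| Constant 20% | 0.160 | 80% / 81% | 87% / 88% | 40 / 19 |
| Constant 10% | 0.090 | 59% / 59% | 67% / 68% | 71 / 33 (protocol) |
| Linear 0–20% (mean 10%) | 0.0867 | 57% / 58% | 66% / 66% | 74 / 35 |
| Linear 0–30% (mean 15%) | 0.120 | 69% / 70% | 78% / 78% | 54 / 25 |
| Linear 0–40% (mean 20%) | 0.147 | 77% / 78% | 85% / 85% | 44 / 21 |

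The same formula gives the odds ratio that could be excluded with 80% power: exp(2.486 × SE), where SE = √[1.25/(cases × v)]. At constant 10% use and 1:4, 40 cases have SE 0.589 and could exclude 4.3-fold. Nineteen cases have SE 0.855 and could exclude 8.4-fold.

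**Step 4: check the approximation.** Simulated 1:4 matched sets (4,000 runs per scenario, conditional logistic score and Wald tests, one-sided 5%) gave 84–85% for 40 cases and 83–86% for 19 cases at constant 20%. With linear 0–20% uptake this fell to 59–64% and 48–66%. The wide range for 19 cases shows how dependent so small a target is on the choice of test.

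**Step 5: the deciding limit.** A one-sided 5% test corresponds to the upper limit of a 90% interval. If the 95% limit (z = 1.960) were used at constant 20% and 1:4, the need would be 51 and 24 cases, and 40 and 19 would give 70% and 71%. With very many controls those become 79% and 80%.

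**The case against.** Several points on the other side stand.

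- **The calculation is right.** A reader might infer that 40 and 19 cases fail to deliver 80% power. On the stated inputs they deliver it.
- **The protocol does not claim 20% use at every index date.** It states one overall figure for the control group. If that is an average over index dates, reached for example by a 0–40% rise, the loss is only about three points.
- **The targets do not cap accrual.** Section 7.2.2.4.1 takes all first-time cases, and data collection ends on a fixed date, 30 September 2019. Reading section 7.7.2 as a stopping rule at 40 or 19 goes beyond the text.
- **The 1:4 ratio is conservative.** All available controls are matched. With very many controls, constant use of 15% would be enough (79.8% and 80.5%).
- **Reporting 95% intervals does not contradict a one-sided 5% test.** Nothing says the margin is judged on the 95% limit, and a plan may leave the decision rule to the SAP.
- **The risk is partly disclosed.** Table 7-6 prints the 10% column, section 7.9 names uptake, and section 7.7.1 tracks LCZ696 users and cases.

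None of this supports calling 20% conservative. Disclosing uptake as the main uncertainty for power undercuts that label. Unlimited controls do not rescue a mean use near 10%, where power stays at or below 68%.

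**Conclusion.** The point holds as an unsupported label attached to an incomplete adequacy criterion. It is not an error of calculation. At 1:4 and one-sided 5%, the 40 and 19 targets carry the stated power only if LCZ696 use averaged over index dates is about 20% or more. Under linear growth from launch, an average of 20% means about 40% use by the end, and nothing in the protocol supports that level. If mean use is near 10%, power is 57–59% at 1:4 and at most 66–68% with unlimited controls.

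These sizes rest on a true odds ratio of 1, the normal approximation and assumed uptake patterns. Actual uptake is not in the document, so the shortfall is conditional. The need to make the targets depend on observed exposure is not. The undefined deciding limit is a secondary ambiguity that is easily closed in the same edit.

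**What to change.** 1. In section 7.5 and the abstract, delete the conservative label for the 20% figure. It can stay for the 1:4 ratio. Present 40/19 as conditional on average use of 20% over index dates, beside 71/33 at 10%.
2. In section 7.7.2, judge the necessary number of cases from LCZ696 prevalence observed in matched controls. Compute the expected standard error of the log odds ratio at OR = 1 as 1/√Σ[pᵢ(1−pᵢ)/(1 + 1/kᵢ)], summed over cases, where pᵢ is the prevalence for that database and calendar period and kᵢ the number of controls. Require at most ln 3/2.486 = 0.442 for the 3-fold margin and ln 5/2.486 = 0.647 for the 5-fold margin.
3. If data collection ends before that is met, analyse all cases and state the odds ratio excludable with 80% power.
4. State that the rule-out is judged on the upper limit of the 90% interval, to match the one-sided 5% test. If the 95% limit is intended, restate power at constant 20% use as about 70%/71% at 1:4 (about 79%/80% with very many controls). The standard error limits then become ln 3/2.802 = 0.392 and ln 5/2.802 = 0.574.

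The cost is wording and a less favourable power statement. Section 7.7.1 already has progress reports counting cases and LCZ696 users; prevalence in matched controls is a small addition.
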